**Table 14 Dose Modification and Stopping Criteria**

Event	Action
Colitis events (e.g. Colitis, ileitis, enterocolitis etc)	
Grade 1	If receiving RXC004, either as monotherapy or in combination with nivolumab; Reduce RXC004 to a lower dose (see Table 15 for dose reduction scheme) and manage as per Appendix J (and Appendix G if applicable)
Grade 2	If receiving RXC004, either as monotherapy or in combination with nivolumab Interrupt RXC004. Manage as per Appendix J and Appendix G if applicable. When event has resolved to Grade 1 a and steroids tapered to $\leq 10$ mg of prednisone per day (or equivalent), resume RXC004 at a lower dose (see Table 15 for dose reduction scheme) and nivolumab (if applicable) at 480 mg q4w. If event re-occurs after re-starting study treatment, then RXC004 and nivolumab (if applicable) should be permanently discontinued.
Grade 3	If receiving RXC004 monotherapy; Interrupt RXC004. Manage as per Appendix J. When event has resolved to Grade 1 a and steroids tapered to $\leq 10$ mg of prednisone per day (or equivalent), resume RXC004 at a lower dose (see Table 15 for dose reduction scheme). If event re-occurs after re-starting study treatment, then RXC004 should be permanently discontinued.
Grade 4	If receiving RXC004 in combination with nivolumab; permanently discontinue both agents and manage as per Appendix J and Appendix G.  If receiving RXC004, either as monotherapy or in combination with nivolumab; Permanently discontinue study treatment (both agents if applicable) . Manage as per Appendix J and Appendix G

Event	Action
Dysgeusia events	
Grade 1/2	RXC004 related; Consider dose reduction, depending on clinical symptoms Manage as per Appendix I Interrupt RXC004 treatment if dysgeusia is associated with >5kg weight loss from baseline
Grade 2 associated with a 10-20% decrease in body weight	RXC004 related; Manage as per Appendix I Reduce RXC004 to a lower dose (see Table 15 for dose reduction scheme).
Grade 2 associated with a >20% decrease in body weight	RXC004 related; Permanently discontinue RXC004. Nivolumab can continue if clinical benefit is judged by investigator.
Other adverse events	
Any event that meets discontinuation criteria for nivolumab (see Appendix G)	Permanently discontinue nivolumab. RXC004 can continue if clinical benefit is judged by investigator.
Any event that meets nivolumab treatment hold (see Appendix G)	Interrupt nivolumab and manage as per Appendix G. Nivolumab can be re-started when event is resolved to ≤Grade 1 and any steroid taper completed (to ≤10 mg prednisone equivalent). RXC004 can continue whilst nivolumab is held if the patient is judged (by the investigator) to be receiving clinical benefit.
Grade 3 toxicity (1 st event)	RXC004 related; Interrupt RXC004 and provide supportive care, resume at a lower dose level when resolved (grade ≤ 2 or returns to baseline). See Table 15 for dose reduction scheme.
	Nivolumab related; See guidelines in Appendix G.
Grade 3 toxicity (subsequent recurrence of a previously experienced event)	RXC004 and/or nivolumab related; Permanently discontinue the related study treatment.

Event	Action
Grade 4 toxicity	RXC004 and/or nivolumab related; Permanently discontinue RXC004 and nivolumab (if applicable)
All Grade events	Study treatment can be interrupted or discontinued for any clinically significant AEs that in the investigator's opinion warrants treatment interrupted or discontinuation.
Bone events	
Confirmed (by imaging) RXC004 related fragility bone fracture (excluding grade 1 vertebral deformities)	Permanently discontinue RXC004. Nivolumab can continue if the patient is receiving clinical benefit as judged by the investigator.
Patients with a DXA scan showing $\geq 7\%$ worsening in BMD at lumbar spine or total hip compared to baseline	Permanently discontinue RXC004. Nivolumab can continue if the patient is receiving clinical benefit as judged by the investigator.
An individual increase in $\beta$ -CTX of CCI pg/ml from the baseline (screening) value or an individual measurement of CCI pg/ml	Permanently discontinue study treatment unless the patient has received clinical benefit (investigator assessment) and continued treatment is warranted.
COVID-19 infection	
Positive COVID-19 test	Interrupt RXC004, until acute symptoms have resolved.
Major surgery	
	Interrupt RXC004, resume at full dose. Nivolumab does not need to be interrupted.
	No stoppage is required for biopsy procedures.
Vomiting	
	If vomiting occurs shortly after RXC004 is swallowed, the dose may be replaced if all of the intact capsules can be counted. Resume with the following scheduled dose.
Missed RXC004 dose	
	Allowed to take the scheduled dose up to 4 hours after the scheduled dose time. If greater than 4 hours, the missed dose should not be taken, and patient should continue with next dose at allotted time.

a Attempts should be made to confirm that the colitis has resolved to Grade  $\leq 1$  (e.g. normalised CRP or fecal calprotectin if raised during event; GI appearance normalised on X-ray/CT or endoscopy) before restarting RXC004.

AE, adverse event; BMD, bone mineral density; COVID-19, Coronavirus disease 2019; QD, once daily.

Toxicity will be assessed utilizing the NCI Common Terminology Criteria for Adverse Event (CTCAE) version 5.0, unless otherwise specified. Every effort should be made to administer trial treatment at the planned dose and schedule. However, patients experiencing RXC004 related toxicities may have their RXC004 dose modified as outlined below.

RXC004 related toxicities observed during the course of the study will be managed by interruption of RXC004 and initiation of appropriate treatment as judged by the Investigator. Upon re-starting treatment the guidance for dose reduction in RXC004 contained in Table 15 should be followed.

Patients in Arm A who have undergone dose reduction during monotherapy cannot have the RXC004 dose re-escalated if switching to RXC004 + nivolumab combination therapy. The RXC004 dose must be discussed with the Sponsor prior to starting combination therapy.

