**Table 15 Guidance for dose reductions for RXC004-related adverse events**

Dose Level	RXC004 (monotherapy)	RXC004 (in combination therapy)
Initial dose level	2 mg QD	1.5 mg QD
1 st dose reduction	
 
Grade 3 toxicity (1st event)
 
Grade 2 dysgeusia associated with 10-20% weight lossa
 
 
Hold RXC004b. Upon resolution to ≤ grade 2, restart at 1.5 mg QD
 
Dose reduce to 1.5 mg QD
	
Hold RXC004b. Upon resolution to ≤ Grade 2, restart at 1.0 mg QD
 
Dose reduce to 1.0 mg QD

2 nd dose reduction	
 
Grade 3 toxicity (1st unique event)
 
Grade 3 toxicity (recurrence of a previously experienced Grade 3-4 event)
 
Grade 2 dysgeusia associated with >20%
 
 
Hold RXC004b. Upon resolution to ≤ grade 2, restart at 1 mg QD
 
Permanently discontinue RXC004
 
Permanently discontinue RXC004
	
Hold RXC004b. Upon resolution to ≤ Grade 2, restart at 0.5 mg QD
 
Permanently discontinue RXC004
 
Permanently discontinue RXC004

Dose Level	RXC004 (monotherapy)	RXC004 (in combination therapy)
weight loss a		
3 rd dose reduction	Not permitted. Permanently discontinue RXC004	Not permitted. Permanently discontinue RXC004

a excluding other possible causes and despite optimal treatment  
 b RXC004 can be resumed after an interruption, as long as no other treatment discontinuation criteria have been met. Patients who experience disease progression whilst RXC004 is held, will not be eligible to be treated beyond progression.

For patients treated with RXC004 and nivolumab, dose reductions in nivolumab are not allowed. Patients experiencing nivolumab related toxicities may delay nivolumab infusions or permanently discontinue nivolumab as described in Appendix G and Table 14.

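### Section 6.6 gives conflicting instructions for RXC004-related Grade 2 dysgeusia with 10-20% weight loss, and its interruption above 5 kg has no usable restart rule

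*Protocol*

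**What the plan says.** Table 14 in Protocol Section 6.6 has three dysgeusia rows.

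- **Grade 1/2.** The action begins "RXC004 related; Consider dose reduction, depending on clinical symptoms Manage as per Appendix I" and then adds "Interrupt RXC004 treatment if dysgeusia is associated with >5kg weight loss from baseline". The row sets no upper limit on weight loss.
- "Grade 2 associated with a 10-20% decrease in body weight". The action is "Reduce RXC004 to a lower dose (see Table 15 for dose reduction scheme"). No hold is mentioned.
- "Grade 2 associated with a >20% decrease in body weight". RXC004 is permanently discontinued.

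Table 15 places "Grade 2 dysgeusia associated with 10-20% weight loss" under the first dose reduction. The monotherapy action is "Dose reduce to 1.5 mg QD", and the combination column has the same form. In the same block, Grade 3 toxicity is held first and restarted lower after resolution. Note a of Table 15 limits its dysgeusia lines to cases where other causes are excluded and treatment has been optimised. The Table 14 rows carry no such condition.

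Two general statements in Section 6.6 also bear on this. Text before Table 14 lets RXC004 be withheld until a related event returns to baseline or to Grade 2 or lower. Text after it says "RXC004 related toxicities observed during the course of the study will be managed by interruption of RXC004 and initiation of appropriate treatment", with Table 15 followed on restart. Appendix I only sends the reader back to Table 14 and Section 6.6.

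**The concern.** One trigger is in kilograms and the other in percent, and no text says which takes precedence or whether the actions add up. Two sites facing the same event could act differently, each with a row to cite.

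The choice has consequences for the patient. Under Table 15 note b and Section 7.1.1, a patient who progresses while RXC004 is on hold cannot be treated beyond progression. A reduction uses one of only two permitted steps, and in Arm A it also bars re-escalation on switching to the combination (Sections 4.1 and 6.6).

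It also affects reporting. Dose reductions, interruptions and the dysgeusia assessment are secondary safety endpoints (Protocol Table 3). SAP Sections 4.10.1 and 4.12.1 tabulate reductions and interruptions separately, so the counts would partly reflect which row a site followed.

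**Working it through.** The plan states no figure to reproduce here. The check puts both triggers on one scale.

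**Inputs**
- Triggers: more than 5 kg; 10-20%; more than 20% (Table 14).
- Dysgeusia has only Grades 1 and 2 (Section 8.3.12), so the Grade 1/2 row covers all related dysgeusia. The 10-20% row needs Grade 2, so the overlap is confined to Grade 2.
- Patients under 40 kg are excluded from the combination (exclusion criterion 16); monotherapy has no stated lower limit.
- The documents give no distribution of body weight. The range of 40 to 100 kg is an assumption.

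**Formulas**, for baseline weight W in kg
- 5 kg as a percentage of baseline = 500/W
- Limits of the 10-20% band in kg = 0.10W and 0.20W
- Share of the band's width above 5 kg = (0.20W − 5)/(0.10W), capped at 1. This is a share of the band, not of patients.

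| W (kg) | 5 kg as % | 10-20% band (kg) | Share of band above 5 kg |
|---|---|---|---|
| 40 | 12.5 | 4.0 to 8.0 | 0.75 |
| 45 | 11.1 | 4.5 to 9.0 | 0.89 |
| 50 | 10.0 | 5.0 to 10.0 | 1.00 |
| 60 | 8.3 | 6.0 to 12.0 | 1.00 |
| 70 | 7.1 | 7.0 to 14.0 | 1.00 |
| 80 | 6.25 | 8.0 to 16.0 | 1.00 |
| 100 | 5.0 | 10.0 to 20.0 | 1.00 |

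The two triggers meet at W = 5/0.10 = 50 kg.

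**Cases**
- 80 kg, loss of 6 kg: 6/80 = 7.5%. Only the Grade 1/2 row applies: interrupt.
- 80 kg, Grade 2, loss of 9 kg: 9/80 = 11.3%. Both rows apply: interrupt under one, reduce under the other and under Table 15.
- 40 kg, Grade 2, loss of 4.5 kg: 4.5/40 = 11.3%. Only the 10-20% row applies: reduce.
- Above 20%, even a 40 kg patient has lost more than 8 kg. Both triggers are met, but permanent discontinuation includes interruption, so no practical conflict arises.

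**Restart after the 5 kg interruption.** The general test is met once the event is at Grade 2 or lower. Dysgeusia cannot exceed Grade 2, so the test is met at onset. Table 15 has no line for a loss above 5 kg but under 10%, so following it on restart yields no dose level. By contrast, the Table 14 rows for Grade 2 colitis, first Grade 3 toxicity and COVID-19 each state when to resume.

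**The case against.** The best defence is the general text after Table 14: interrupt first, then use Table 15 on restart. Read that way, or with both rows applied together, a patient above 50 kg is interrupted beyond 5 kg, interrupted and restarted lower at 10-20%, and discontinued beyond 20%. Nothing makes the rows mutually exclusive, and neither table says that a reduction must be made without a hold. Note a could also mark the Table 15 reduction as a later step, after other causes are excluded and treatment has been tried.

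This is a fair reading, and it means the conflict is not beyond rescue. But the dysgeusia rows do not state it. Table 15 writes a hold for Grade 3 toxicity and a plain reduction for the 10-20% band in the same block, which does not fit a universal interrupt-first rule. Nor does this reading supply a restart condition or dose level for the 5 kg trigger.

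A reader might infer that the rows run in reverse order, with the stronger action for the smaller loss. Row by row, a loss above 5 kg but under 10% does interrupt while the larger loss only reduces. The documents, however, do not rank interruption above reduction: an interruption can be temporary, whereas a reduction uses a limited step. Under the sequential reading the inversion disappears.

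The effect on reporting is also modest. Reductions and interruptions are summarised descriptively with reasons (SAP Section 4.10.1), and the arms are not formally compared (SAP Section 4.2.6). Table 14 already allows interruption for any clinically significant event on the investigator's opinion, so these counts depend on judgement anyway.

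**Conclusion.** The conflict stands. For a patient above 50 kg at baseline with RXC004-related Grade 2 dysgeusia and 10-20% loss, Section 6.6 supports both interruption and direct reduction. Between 40 and 50 kg the overlap is partial (75% of the band at 40 kg, 89% at 45 kg). The missing restart rule after the 5 kg interruption does not depend on how the overlap is resolved.

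It would be wrong to infer that every patient above 50 kg is exposed: the conflict needs both Grade 2 dysgeusia and at least 10% loss. Among Phase 1 DLT-evaluable patients, related Grade 2 dysgeusia occurred in 1/6 at 2 mg monotherapy (Table 4) and 2/6 at 1.5 mg with nivolumab (Table 8). If those rates carried over to 20 evaluable patients per arm, about 20 × 1/6 = 3 and 20 × 2/6 = 7 would have it, before any weight-loss condition. The denominators are very small, and the documents do not say how often weight loss of this size accompanies dysgeusia, so this is only an order of magnitude.

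The effect is on patient safety and on descriptive counts of interruptions and reductions. The primary analyses of DCR and ORR are not directly affected.

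**What to change.** Reconcile the Table 14 dysgeusia rows, Table 15 (including note a) and the two general statements in Section 6.6, before and after Table 14. Each weight-loss level should have one stated action, or one stated sequence if the steps are meant to follow each other. State whether note a applies to the Table 14 rows. Give the interruption above 5 kg a restart condition that an event capped at Grade 2 does not meet at onset, and a restart dose level. Which thresholds, actions and doses apply is a clinical decision for the sponsor.

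The cost is clarifying wording in one protocol section. Sample size and primary analyses are unchanged. For events already managed under the current text, the recorded reasons for reduction and interruption can be read alongside the counts.

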Once Arm B is opened, patients who are eligible for both Arm A and Arm B will be randomised 2:1 to Arm B: Arm A in an open-label manner on Day 1. Randomisation will be stratified by genetic alteration (RNF43, RSPO).

a A baseline (pre-first dose IP) biopsy is a mandatory requirement, except in exceptional circumstances where biopsy is not technically feasible. All patients without a baseline sample must be approved by Sponsor before starting study treatment. The baseline [CC1] can be a 'fresh newly acquired' biopsy or an [CC1] (preferably from the same organ site that 'on treatment' biopsy will be taken) and taken after completion of all prior standard of care treatments. In exceptional circumstances where baseline biopsy cannot be scheduled before C0D1, the procedure may be performed before C1D1 after a minimum of 4 days washout from C0D1. A second 'on treatment' biopsy at Cycle 1 Day 15 (+/- 1 day), is also mandatory providing that investigator judges the second biopsy to be technically and clinically feasible. The Cycle 1 Day 15 biopsy should be collected post-dose and the time of collection should be accurately recorded. RECIST 1.1 target lesions should not be chosen for biopsies.

b [CC1]

c Triplicate ECGs should be collected as follows;

Cycle 0: [CC1]

Cycle 1, [CC1]

Cycle X, [CC1]

At selected sites, ambulatory Holter monitoring will be used on Cycle 0 Day 1 and Cycle 1 Day 15 for central analysis of digital ECG information.

d [CC1]

e [CC1]

[CC1]

f Blood samples for PK analysis should be collected as follows (the actual time for each blood draw must be accurately recorded);  
Cycle 0: CCI  
Cycle 1, CCI  
Cycle X, CCI

g CCI

h ECGs are required at C2D1 and as clinically indicated from C3D1 onwards

i CCI

CCI

CCI

j RXC004 + nivolumab combination treatment will be allowed for up to 20 patients that have progressed on RXC004 monotherapy. This treatment phase will only be opened after the RP2D for RXC004 + nivolumab is determined

k Patients that consent to RXC004 + nivolumab combination treatment will have eligibility re-assessed for RXC004 + nivolumab combination specific criteria

l One 'on treatment' biopsy is required during cycle 3 of RXC004 monotherapy or RXC004 + nivolumab combination treatment, providing that investigator judges the biopsy to be technically and clinically feasible. The biopsy should be collected post-dose and the time of collection should be accurately recorded.

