## **6.6 Dose Modification**

RXC004 dose reduction and interruption are permitted. Nivolumab dose reduction is not permitted but dose interruption/delay is permitted as per Appendix G.

RXC004 may be dose interrupted (withheld) until a clinically significant (any grade) and/or a grade  $\geq 3$  related adverse event resolves to baseline or  $\leq$  grade 2. RXC004 may also be withheld if it is necessary to give a concomitant medication that is a moderate or strong CYP3A4 inhibitor. RXC004 related colitis events should be managed as per Appendix J.

Adverse events that are assessed as being causally related nivolumab should be managed as per the Nivolumab Toxicity Management and Dose Modification Guidelines (Appendix G). If either agent is interrupted or discontinued for a related-AE the other agent (nivolumab or RXC004) may be continued if the patient is judged (by the investigator) to be receiving clinical benefit.

RXC004 and nivolumab dose interruption and stopping criteria are detailed in Table 14.

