## 8 STUDY ASSESSMENTS AND PROCEDURES

- Study procedures and their timing are summarised in the SoA. Protocol waivers or exemptions are not allowed.
- Immediate safety concerns should be discussed with the sponsor immediately upon occurrence or awareness to determine if the participant should continue or discontinue study intervention.
- Adherence to the study design requirements, including those specified in the SoA, is essential and required for study conduct.
- All screening evaluations must be completed and reviewed by Investigator to confirm that potential participants meet all eligibility criteria. The investigator will maintain a screening log to record details of all participants screened and to confirm eligibility or record reasons for screening failure, as applicable.
- Procedures conducted as part of the participant's routine clinical management (e.g., blood count) and obtained before signing of the ICF may be utilised for screening or baseline purposes provided the procedures met the protocol-specified criteria and were performed within 28 days of the first dose of study treatment.
- The maximum amount of blood collected from each participant over the duration of the study, is expected to not exceed 500 mL.

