	Grade 3 or 4	
Admit patient and perform investigations as per Grade 2.
 
Treat with (methyl)prednisolone IV 2-4 mg/kg/day and cover with empiric antibiotics. Once improved to baseline wean steroids over at least 8 weeks. If no improvement after 48hrs add infliximab 5 mg/kg (or MMF if concurrent hepatic toxicity).
 
High resolution CT +/- bronchoscopy and BAL pending appearances
 
Permanently discontinue

Hepatitis	Grade 1: ALT or AST >ULN-3XULN	
If > ULN-3XULN repeat in 1 week
 
Continue treatment

	Grade 2: ALT or AST 3-5XULN	
Re-check LFTs/INR/albumin every 3 days. Review medications, e.g. statins, antibiotics and alcohol history. Perform liver screen: Hepatitis A/B/C serology, Hepatitis E PCR, anti-ANA/SMA/LKM/SLA/LP/LCI, iron studies
 
If rising ALT/AST when re-checked start oral prednisolone 1 mg/kg. Once resolved to Grade 1, wean steroids over 2 weeks. Re-escalate if worsening; nivolumab treatment may be resumed once prednisolone <math>\leq</math> 10 mg

Adverse Event	Severity	Investigations, Treatment and Dose modification
		
Consider imaging for metastases/clot
 
Withhold dosea
 
Grade 3:AST or ALT 5-20XULN
 
Re-check LFTs/INR/albumin every day. Other investigation as per Grade 2.
 
If ALT/AST < 400 and normal bilirubin/INR/albumin treat with oral prednisolone 1 mg/kg. If ALT/AST > 400 or raised bilirubin/INR/low albumin treat with i.v. (methyl)prednisolone 2 mg/kg. Once improved to G2, can change to oral prednisolone and wean over 4 weeks
 
Perform US with Doppler. Low threshold to admit if clinical concern
 
Permanently discontinue

	Grade 4: ALT or AST >20xULN	
Investigations as per Grade 3
 
Treat with i.v. (methyl)prednisolone 2 mg/kg. If condition worsens despite steroids, add mycophenolate mofetil (MMF) 500-1000 mg bd. If worse on MMF, consider addition of tacrolimus.
 
Hepatology consult and consider liver biopsy
 
Permanently discontinue

Hypophysitis	Grade 2	
Pituitary axis assessment, MRI pituitary protocol (also exclude brain metastases), visual field assessment. Monitor TFTs.
 
Start oral prednisolone 0.5-1 mg/kg od after pituitary axis assessment. If no improvement in 48h, treat as severe with i.v. (methyl)prednisolone. Wean steroids based on symptoms over 2-4 weeks to 5 mg prednisolone. Do not stop steroids
 
Refer to or consult endocrinologist
 
Withhold dosec

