Other	Other Grade 3AEs - First occurrence - Recurrence of same Grade 3 adverse events	
Withhold dosea
 
Permanently discontinue

	Life-threatening or Grade 4 adverse reaction	Permanently discontinue
	Grade 3 myocarditis	If myocarditis is suspected, admit the patient and immediately start high-dose (methyl)prednisolone (1-2 mg/kg). In the case of deterioration, consider

Adverse Event	Severity	Investigations, Treatment and Dose modification
		
adding another immunosuppressive drug (MMF or tacrolimus)
 
Permanently discontinue
 
Guillain-Barré syndrome (GBS)
 
Nerve conduction studies (acute polyneuropathy) Lumbar puncture (elevated protein with normal WBC count). Pulmonary function tests with vital capacity and maximum inspiratory/expiratory pressures. Antibody testing for GBS variants, e.g. GQ1b in Miller Fisher variant
 
Use of steroids not recommended in idiopathic GBS If no improvement or worsening, plasmapheresis or intravenous immunoglobulin indicated.
 
Neurological consult. Consider location of care where ventilatory support available (required in 15%-30% idiopathic cases)
 
Permanently discontinue

	Myasthenia Gravis	
Check for ocular muscle and proximal muscle fatigability. AChR and anti-MuSK antibodies Bedside tests, e.g. Tensilon test or ice pack test with neurological input. Repetitive nerve stimulation and single fibre EMG
 
Steroids indicated (oral or i.v. depending on symptoms). Pyridostigmine initial dose 30 mg tds. If no improvement or worsening, plasmapheresis or IVIG may be considered Additional immunosuppressants azathioprine, cyclosporine, mycophenolate Avoid certain medications, e.g. ciprofloxacin, beta-blockers, that may precipitate cholinergic crisis
 
Neurological consult
 
Permanently discontinue

	Requirement for 10 mg per day or greater prednisone or equivalent for more than 12 weeks	Permanently discontinue
	Persistent Grade 2 or 3 adverse event lasting 12 weeks or longer	Permanently discontinue

a Resume treatment when adverse reaction improves to Grade 0 or 1

b Other immunosuppressive treatment options – MMF 500-1000 mg bid or tacrolimus

c Withhold dose until symptoms resolve and any steroid treatment is complete. Treatment should be continued in the presence of hormone replacement therapy as long as no symptoms are present

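### After a non-colitis Grade 4 event related only to nivolumab, one Table 14 row and Section 6.6 permit RXC004 to continue although the Grade 4 row requires both drugs to stop; nothing expressly limits the permission

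*Protocol*

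**What the plan says.** The point concerns patients receiving RXC004 with nivolumab: Arm B, and Arm A patients who cross over after progression. Table 1 note j says "RXC004 + nivolumab combination treatment will be allowed for up to 20 patients that have progressed on RXC004 monotherapy".

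- **Section 6.6, body text:** "If either agent is interrupted or discontinued for a related-AE the other agent (nivolumab or RXC004) may be continued", provided the investigator judges that the patient is benefiting. The section then refers to Table 14 for the interruption and stopping criteria.
- **Table 14, event meeting the Appendix G nivolumab discontinuation criteria:** nivolumab stops permanently, and "RXC004 can continue if clinical benefit is judged by investigator".
- **Table 14, Grade 4 toxicity:** for an event related to RXC004, nivolumab or both, "Permanently discontinue RXC004 and nivolumab (if applicable".
- **Table 14, recurrent Grade 3 toxicity:** "Permanently discontinue the related study treatment".
- **Appendix G, Table 19:** permanent nivolumab discontinuation for "Life-threatening or Grade 4 adverse reaction", and in organ-specific rows such as hepatitis, "Grade 4: ALT or AST >20xULN".
- **Section 7.1:** a patient receives no further investigational product after an adverse event that meets the discontinuation criteria of Appendix G or Table 14.
- **Section 8:** "Immediate safety concerns should be discussed with the sponsor immediately upon occurrence or awareness". It also rules out protocol waivers.

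**The concern.** The nivolumab-discontinuation row and the Grade 4 row sit in the same block of Table 14. Both are triggered by the same event, and they treat RXC004 differently: one leaves it to the investigator's judgement of benefit, the other ends it. Neither row mentions the other. An investigator who starts from Appendix G, finds that nivolumab must stop, and then reads the matching Table 14 row would conclude that RXC004 may continue. That conclusion breaches the Grade 4 row.

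What is at stake is the safety of an individual patient after a Grade 4 event, that patient's RXC004 exposure, and the RXC004 discontinuation counts that form part of the secondary safety endpoint. Because waivers are not allowed, continuing RXC004 under the permissive row could also be recorded as a protocol deviation.

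**Working it through.** The plan states no figure on this point, so the main check is a comparison of the rules.

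**1. Does one event meet both rows?** Take a combination patient with hepatitis and ALT or AST above 20 times the upper limit of normal, attributed to nivolumab alone. Table 19 stops nivolumab, so the nivolumab-discontinuation row applies. The event is also Grade 4 and nivolumab related, so the Grade 4 row applies.

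| Text | Trigger met? | RXC004 | Grade 4 exception stated? |
|---|---|---|---|
| Table 14, nivolumab discontinuation | Yes | May continue if benefit is judged | No |
| Section 6.6 sentence | Yes | May continue if benefit is judged | No |
| Table 14, Grade 4 toxicity | Yes | Permanently discontinued | Not applicable |

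**2. Can the Grade 4 row be read as stopping only the causal drug?** No. Elsewhere in Table 14, for example under Grade 2 colitis, the qualifier about applicability means that the patient is receiving nivolumab. Where the authors meant the causal drug only, in the recurrent Grade 3 row, they used different words: "Permanently discontinue the related study treatment".

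**3. Does Section 7.1 settle it?**
- Read as ending all investigational product, it stops both drugs. That reading would also cancel the nivolumab-discontinuation row's permission for every event, so it is unlikely to be what was meant.
- Read drug by drug, RXC004 still meets a stopping criterion of its own, through the Grade 4 row.
- Both readings favour stopping RXC004. But the section points back to Table 14 and does not say that the permission yields.

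**4. Where is there no conflict?**
- Grade 4 colitis: Table 14 and Appendix J both stop both drugs.
- Grade 3 colitis on the combination, and colitis recurring after restart under the Table 14 and Appendix J rules: both drugs stop.
- Non-colitis nivolumab stops below Grade 4, such as Grade 3 hepatitis: the Grade 4 row is not triggered, so the permission can operate.

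**5. Reverse case.** After a Grade 4 event related only to RXC004, the Section 6.6 sentence lets nivolumab continue, while the Grade 4 row stops both.

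**6. Size.** Table 9 (Phase 1 combination module) reports treatment-emergent events of Grade 4 or higher in 0 of 5 patients at 1.0 mg and 0 of 8 at 1.5 mg, so 0 of 13. The exact one-sided 95% upper bound for 0 of n is 1 − 0.05^(1/n):
- n = 13: 1 − 0.05^(1/13) = 0.206, or 20.6%.
- n = 8 (the dose used here): 1 − 0.05^(1/8) = 0.312, or 31.2%.

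These bounds cover all Grade 4 or higher treatment-emergent events, a wider class than non-colitis events related only to nivolumab.

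**The case against.** The strongest reply is that a permission has met a mandate. Nobody is told to keep giving RXC004, stopping both drugs satisfies every passage, and a specific mandatory stop ordinarily limits a general permission. Section 6.6 itself defers to Table 14, Section 7.1 leans the same way, and the Grade 4 colitis rule follows the same pattern. Sponsor discussion of immediate safety concerns is a further safeguard.

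Much of this stands. A reader might infer that the protocol gives two orders that cannot both be obeyed, or that it offers no guidance on which prevails. The documents support neither inference. What remains is that the permission covers any event meeting the nivolumab stop criteria, is repeated in the body text, and carries no Grade 4 exception. The sponsor contact supplies no rule.

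The objection on size also stands. Table 9 counts 4 of 13 patients with treatment-related events of Grade 3 or higher, and the same number, 4 of 13, with RXC004-related ones. The accompanying text describes none attributed to nivolumab alone. The single drug-induced liver injury was attributed to both drugs. A reader might also infer a sizeable chance that the conflict arises in this trial. With 20 combination patients, 1 − (1 − p)^20 gives 18%, 33% and 64% at p = 1%, 2% and 5%, but those rates are pure assumptions and the documents give no basis for choosing among them. Counting 40 patients would require every one of the 20 crossover places to be filled, against an Arm A target of 20 evaluable patients and a requirement for progression at the week-8 scan.

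Finally, the Version 6.0 change log might suggest that the Grade 4 stop was meant only for RXC004-related events. The log is not operative text, and the current row expressly includes nivolumab-related events.

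**Conclusion.** Wrong as written, within a narrow scope: combination-treated patients with a non-colitis Grade 4 event related only to nivolumab. One Table 14 row and Section 6.6 permit RXC004 to continue, while another Table 14 row requires it to stop. The better reading is that both drugs stop, but it has to be inferred, and following the permission as written breaches a mandatory safety stop.

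The conclusion rests on the text alone and needs no assumed event rate. Affected patients are likely to be few: 0 of 13 had any Grade 4 or higher treatment-emergent event in Phase 1, although so small a sample cannot exclude them, and the rate for the affected subset is not given. Endpoint definitions, sample size and the scan schedule are not affected.

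A reader might also infer that the permission applies freely to every nivolumab stop below Grade 4. It does not: colitis has its own rules, and some of those stop both drugs below Grade 4.

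**What to change.** Add the same clause in two places, the Table 14 nivolumab-discontinuation row and the Section 6.6 sentence on continuing the other agent: *except treatment-related Grade 4 events, for which both agents are permanently discontinued*. In Section 6.6 the clause also covers the reverse case, where nivolumab might otherwise continue after a Grade 4 event related only to RXC004. The permission for non-colitis nivolumab stops below Grade 4 is untouched. Section 7.1 needs no edit.

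The cost is two clauses, with no change to sample size, visits, endpoints or analyses. The downside is that some patients lose RXC004 after a Grade 4 event caused by nivolumab alone, which the Grade 4 row already requires.

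The conflict could instead be removed by rewording the Grade 4 row to stop only the related drug, as the recurrent Grade 3 row does. That would loosen an existing safety rule, so it is a trade-off for the sponsor to justify and should not be the default.
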